8.1 Prohibited Medications or Therapies

Prohibited medications or therapies during the study include:

- Topical product other than the assigned treatment (including moisturizers, sun screen, creams, ointments, lotions, powders, or gels of any kind and new brands of make-up) within the selected treatment area within one day prior to the Baseline Visit.
- Topical medications: corticosteroids, alpha hydroxy acids (e.g., glycolic acid, lactic acid, etc. >5%), beta hydroxy acid (salicylic acid >2%), urea >2%, 5-fluorouracil, diclofenac, imiquimod, ingenol mebutate, ALA or prescription retinoids (e.g., tazarotene, adapalene, tretinoin), OTC products labeled as scrubs of any kind which are used to smooth the skin (as they contain some form of exfoliant such as nut shells, coffee grounds, polymer particles, etc.) within the selected treatment area (face or bald scalp) within one month prior to the Baseline Visit.
- Cryodestruction or chemodestruction, curettage, PDT, surgical excision, or other treatments for AK within the selected treatment area (face or bald scalp) within one month prior to the Baseline Visit.
- Systemic corticosteroid therapy (includes intramuscular administration, see [Section 8.2](#) for guidance regarding intra-articular corticosteroids), interferon, cytotoxic drugs, immunomodulators, immunosuppressive therapies, or retinoids within one month prior to the Baseline Visit.
- Oral isotretinoin within six months prior to the Baseline Visit.
- Chemical peels, including but not limited to alphahydroxy acid, betahydroxy acid, bichloroacetic acid, trichloroacetic acid, and phenol within the selected treatment area (face or bald scalp) within six months prior to the Baseline Visit.

- Dermatologic procedures or surgeries such as: laser resurfacing, PUVA therapy, UVB therapy, or dermabrasion within the selected treatment area (face or bald scalp) within six months prior to the Baseline Visit.
- Areas treated with the test article should not be covered with any type of bandage or occlusive dressings.

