9.1 Visit 1 (-30 to Day 1): Screening/Baseline

Informed consent may be collected from study subjects up to 30 days before Visit 1. If applicable, qualified subjects can washout from prohibited medications or treatments (see [Section 8.1](#)) prior to their Screening/Baseline Visit once informed consent has been obtained. If washout period exceeds 30 days, re-consent is required. The Screening and Baseline Visit may be completed on the same day, if no washout is required.

At this visit, the investigator or designee will:

- Obtain a signed, written informed consent, and update the Subject Screening and Enrollment Log.
- Confirm the subject meets the inclusion/exclusion criteria.
- Document the information required on the Medical History form.
- Document the information required on the Demographics form.
- Record the subject's prior and/or concomitant medications and therapies/procedures.

If the subject requires washout from previous medications, the remaining activities will be performed after washout is completed and must be completed within 30 days of first visit, or the subject needs to be re-consented.

- Perform a dermatologic exam. Consistent with Exclusion Criterion #18, any subject with a suspicious lesion within the treatment area should not be enrolled prior to confirmation that the lesion is not skin cancer. In the event that a biopsy is warranted to make such a determination per the investigator, such a procedure is considered outside the scope of this study and therefore will be the responsibility of the potential subject. In the event that a biopsy is needed and it is not available for review, the subject shall be considered a screen failure.
- Identify the 25 cm² treatment area on either the face (excluding ears) or bald scalp. NOTE: Use the procedure as detailed in the Treatment Area Identification Manual to create and label the transparency to record the designated treatment area.
- Create a "subject specific" template per the instructions provided in the Treatment Area Identification Manual to assist the subject in the identification of the treatment area prior to application of the test article. A copy of the template will also be retained in the subject's site file for use by the site to properly identify the treatment area at future visits.

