14.2 Adverse Event Details

AEs may be either spontaneously reported or elicited during questioning and examination of a subject. All AEs must be recorded on the AE CRF. If known, the investigator should report the diagnosis of the underlying illness or disorder, rather than its individual symptoms. Subjects experiencing AEs that cause interruption or discontinuation of test article or those experiencing AEs that are present at the end of their participation in the study should receive follow-up as appropriate. AEs should be followed to resolution or stabilization (if possible) and, if they become serious, reported as serious adverse events (SAEs, see [Section 14.3](#)). If possible, the outcome of any AEs that caused permanent discontinuation or that were present at the end of the study, especially those considered by the investigator to be related to the test article, should be reported.

Information on the medical condition of subjects should begin following the subject's written consent to participate in the study and a medical history should be taken at screening. During any wash out and baseline periods, any changes in the health of subjects should be recorded as changes in medical history unless an event occurred as a result of a study-related procedure and is unanticipated; in such cases, the event should be recorded as an AE and reported to the Institutional Review Board (IRB) as an "unanticipated problem" in accordance with local procedures. Other changes in subject health information becomes AE data when the subject begins dosing with the test article; therefore, AE data should be collected from the date of the first dose of test article until the date of the final study visit. These data are considered treatment-emergent AEs.

The investigator will instruct the subject to report any AEs that may occur during the study. At each visit, the investigator should ask the subject, in non-directive fashion, about any change in the subject's overall health status since the previous visit.

The severity of each AE, as judged by the investigator, will be recorded on the appropriate AE CRF and will be graded according to the following scale:

Mild - The AE is usually transient and may require only minimal treatment or therapeutic intervention. The event does not generally interfere with usual activities of daily living.

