Moderate - The AE is usually alleviated with additional specific therapeutic intervention. The event interferes with usual activities of daily living, causing discomfort, but poses no significant or permanent risk of harm to the research participant.

Severe - The AE interrupts usual activities of daily living or significantly affects clinical status, or may require intensive therapeutic intervention.

The investigator must determine the relationship of the AE to the test article according to the following categories:

- Important medical events; a medical event(s) that may not result in death, be life-threatening, or require hospitalization but, based upon appropriate medical judgment, may jeopardize the subject and may require medical or surgical intervention to prevent one of the outcomes listed in the definition above. Examples of such medical events include allergic bronchospasm requiring intensive treatment in an emergency room or at home, blood dyscrasias or convulsions that do not result in inpatient hospitalization, or the development of drug dependency or drug abuse.

Events NOT considered to be serious AEs are:

- Hospitalizations for the treatment, which was elective or pre-planned, of a pre-existing condition that did not worsen, and
- Treatment on an emergency, outpatient basis, for an event not fulfilling any of the definitions of “serious” given above and not resulting in hospital admission.

AEs classified as “serious” by either the investigator or the Sponsor require expeditious handling and reporting to [REDACTED] to comply with regulatory requirements. **All SAEs, whether related or unrelated to test article, must be immediately reported by telephone to the Medical Monitor and, in the event that he/she is unavailable, to the Project Manager listed on the first page of the protocol.** Written notification of all SAEs should be sent to the Project Manager by email or confirmed facsimile transmission. These include those SAEs listed in the protocol or RLD Package Insert and must include an assessment of whether there is a reasonable possibility that the drug caused the event.

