7.2 Safety and Baseline Measurements

7.2.1 Adverse Events

An AE is defined as any untoward medical occurrence associated with the use of a drug in humans, whether or not considered drug related. A treatment emergent AE (TEAE) is defined as an AE that started on or after the date of the first dose of test article.

Serious adverse events (SAE) are defined as an AE or suspected adverse reaction that in the opinion of either the Investigator or Sponsor results in death, is life-threatening, requires inpatient hospitalization or prolongation of existing hospitalization, results in persistent or significant incapacity or substantial disruption of the ability to conduct normal life functions, or is a congenital anomaly/birth defect, or important medical events defined in the protocol.

The severity of an AE will be recorded as mild, moderate or severe. The relationship between an AE and the test article will be classified as related, possibly related or not related. The AE outcome will be specified as not recovered/resolved, recovered/resolved, recovered/resolved with sequelae, recovering/resolving, fatal, or unknown.

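### Before the first dose, a harm caused by a study procedure becomes an AE only if it was unanticipated, so a foreseeable serious one has no visible route to SAE reporting

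*Protocol*

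**What the plan says.** Protocol 14.2 sets the rule for the time between consent and the first dose. The default is that "any changes in the health of subjects should be recorded as changes in medical history". The only exception is "unless an event occurred as a result of a study-related procedure and is unanticipated". An event that meets the exception is recorded as an AE and, in the same sentence, sent to the IRB as an unanticipated problem. For everything else, "AE data should be collected from the date of the first dose of test article until the date of the final study visit".

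Protocol 9.1 allows that, once consent is given, "qualified subjects can washout from prohibited medications or treatments", for up to 30 days, or longer with re-consent. The list in Protocol 8.1 is mostly topical products and local procedures, but one entry covers systemic corticosteroids together with "interferon, cytotoxic drugs, immunomodulators, immunosuppressive therapies, or retinoids within one month prior to the Baseline Visit".

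On escalation, Protocol 14.2 says that AEs are followed and, "if they become serious, reported as serious adverse events". The SAE text that follows says "All SAEs, whether related or unrelated to test article, must be immediately reported by telephone to the Medical Monitor". SAP 7.2.1 reads "Serious adverse events (SAE) are defined as an AE or suspected adverse reaction" and goes on to the usual seriousness criteria.

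**The concern.** Whether an event was anticipated is a sensible test for an IRB unanticipated-problem report. Section 14.2 also makes it a condition for recording the event as an AE at all. These are different questions. A harm can be foreseeable and still be serious, caused by taking part in the study, and something the Medical Monitor should hear about while enrolment continues at about 28 sites.

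The clearest example is a subject who stops a systemic therapy in order to qualify and then has a foreseeable flare that leads to hospitalisation. If the investigator judges the flare to be anticipated, the rule sends it to medical history.

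What is at stake is expedited reporting and the labelling of study-caused harm before dosing. The comparison between products is not at stake.

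**Working it through.** No figure in the plan bears on this point and no arithmetic applies. The check is whether the passages, read together, give a serious, anticipated, pre-dose event any way into SAE reporting.

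**Step 1: apply the 14.2 rule to each kind of pre-dose event.**

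| Event after consent, before first dose | Recorded as | SAE if serious? |
|---|---|---|
| Caused by a study procedure, unanticipated | AE, plus IRB report | Yes |
| Caused by a study procedure, anticipated | Medical history | No visible route |
| Not caused by a study procedure | Medical history | No visible route |

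Seriousness appears nowhere in the rule, so it cannot move an event from one row to another.

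**Step 2: place washout harm.** Section 14.2 refers to washout as a period and to study-related procedures separately, and defines neither procedure nor unanticipated. If stopping a therapy counts as a study-related procedure, anticipated washout harm falls in the second row. If it does not, all washout harm falls in the third row. Both rows end in medical history.

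**Step 3: look for another way into SAE reporting.**
- The escalation wording in 14.2 starts from an AE, and so does the SAP 7.2.1 definition. (That definition also admits suspected adverse reactions, but Protocol 14.1 defines those as a kind of AE.)
- The telephone rule covers SAEs whatever their relationship to test article, but only events that are already SAEs.
- The SAE text gives an end to the collection period, 30 days from the last use of test article, and no start at consent.
- Section 14.4 sends laboratory results that meet the SAE criteria to SAE reporting, but it covers laboratory results only.
- The duty to follow IRB procedures for other safety information leads to the IRB, not to the Medical Monitor.

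**Step 4: trace where the event would appear in the outputs.** SAP 8.5.2 lists medical history for the Safety population, which under SAP 8.2.1 requires randomization and at least one dose. A subject harmed in washout and later dosed therefore appears in that listing. A subject harmed in washout who is never randomized would surface at most as a screen failure with a reason, under SAP 8.4.

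**Step 5: compare with the Schedule of Events.** Both documents mark Adverse Events at Visit 1. Protocol 9.1 lists no AE query at that visit, and 14.2 starts AE collection at the first dose. The mark does not change the recording rule, but the passages do not agree.

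**Step 6: judge the exposure.** Protocol 8.1 has seven entries with a look-back period before Baseline. Five are confined to the selected treatment area (two for topical products, three for local procedures) and two are systemic. The documents give no count of subjects who need any washout.

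**The case against.** The strongest reply is that part of the text cannot be seen. The opening of 14.3, with the start of the SAE definition, is lost from the extracted text, and a rule on when SAE collection begins could stand there. A reader might infer that these events never reach SAE reporting. The documents do not support that. They support only that the readable text gives no route.

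A second reply is that unanticipated is undefined. Protocol 14.1 treats greater severity or specificity as making an event unexpected, although by reference to the reference product's package insert. An investigator reasoning in the same way could call a hospitalisation unanticipated and record an AE. That is possible, but reporting would then depend on individual judgement at each site. The gap remains for events judged anticipated.

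A third reply is that nothing is hidden. A reader might infer that the events are invisible, but 14.2 has them recorded as medical history, and for dosed subjects the SAP lists that history. This stands. What is missing is the AE label and the expedited report, together with any planned medical-history output for subjects never dosed.

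A fourth reply is that the exposed group is tiny. Entry requires immunocompetence and good general health, exclusion criterion 7 bars subjects taking immune-suppressing medication, and the investigator may exclude anyone for whom participation is unsafe. This largely stands. Exclusion criterion 14 is limited to the month before Baseline, however, so stopping such a therapy first is not barred.

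Finally, the safety objective concerns the study products, and pre-randomization events cannot inform a comparison between them. That is correct, and it is why the point bears on subject protection and not on inference.

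**Conclusion.** The point holds as a defect in the recording rule. A foreseeable harm from a study procedure after consent, serious or not, is recorded only as medical history. Washout harm is treated the same way, except where washout is read as a study-related procedure and the harm is judged unanticipated. The readable text gives no route from medical history to the Medical Monitor.

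The number affected is unknown and probably small. A reader might multiply the approximately 600 subjects by an assumed share needing washout: 10% to 30% would give 0.10 × 600 = 60 to 0.30 × 600 = 180. The documents do not support using that range as the size of the problem. The share has no source, it counts topical and local washouts, and it starts from enrolled subjects when someone harmed in washout may never be enrolled.

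TEAE tables are unaffected because SAP 7.2.1 counts from the first dose, and efficacy is unaffected. The conclusion assumes that the lost opening of 14.3 does not start SAE collection at consent or otherwise override 14.2. It is a cheap improvement and does not threaten the trial's conclusions.

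**What to change.** First check the full text of 14.3 for a rule on when SAE collection starts. If there is none, make these changes:

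- **Protocol 14.2.** State that any event after consent that results from a study-related procedure, expressly including washout undertaken to meet the entry criteria, is recorded as a non-treatment-emergent AE whether or not it was anticipated and, if serious, is reported under 14.3. Keep unanticipated only as the condition for the IRB report. Deleting the words about anticipation is not enough, because washout might still not be read as a procedure.
- **Schedule of Events and Protocol 9.1.** Reconcile the Adverse Events mark at Visit 1 with the revised rule, in the SAP's copy of the schedule as well.
- **SAP 8.8.1.** List these events separately from TEAEs, and include subjects who were never dosed.

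The cost is one rewritten sentence in 14.2, a small alignment in the schedule, one listing in the SAP, and a few more AE forms during screening. No washout or treatment rule changes, and no analysis of efficacy or TEAEs changes.

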14.4 Laboratory Test Abnormalities

Although there are no specific labs required in this study, if an abnormal laboratory result indicated as clinically significant by the investigator is the reason for a subject being withdrawn from the study or requires treatment for the abnormality, this abnormal result must also be reported as an AE. In addition, any laboratory test result that meets the criteria for a SAE (see Section 14.3) must also be reported as a SAE so [REDACTED] can collect additional information about that abnormality, including information regarding relationship to test article or other causes, any action taken, and outcome.

14.5 Pregnancy

WOCBP include any female who has experienced menarche or is 10 years of age or older and who has not undergone successful surgical sterilization (hysterectomy, bilateral tubal ligation [at least six months prior to initiation of treatment], or bilateral oophorectomy) or is not postmenopausal (defined as amenorrhea >12 consecutive months in women 50 years of age and older). Even women who are using one of the effective forms of birth control per protocol will be considered of childbearing potential.

WOCBP must have a UPT prior to study enrollment and must use an effective¹⁹ method of birth control during the course of the study, in a manner such that risk of failure is minimized. Prior to study enrollment, WOCBP must be advised of the importance of avoiding pregnancy during the study and the potential risk factors for an unintentional pregnancy. The subject must sign an informed consent form documenting this discussion.

WOCBP should be instructed to contact the investigator immediately if they suspect they might be pregnant (e.g., missed or late menstrual period). If a subject or investigator suspects that a subject may be pregnant at any time during the study, the test article must be withheld until the results of laboratory pregnancy testing are available. If pregnancy is confirmed, the subject must not receive or apply further test article and must be discontinued from the study.

If following initiation of study treatment, it is subsequently discovered that a study subject was pregnant or may have been pregnant at the time of test article exposure, the investigator must immediately notify the Medical Monitor of this event, and record the

¹⁹ Effective forms of birth control include a) hormonal contraceptives [oral, injectable, transdermal or intravaginal] for one full cycle (e.g., four to eight weeks), or IUD for one week, for injectable (e.g., Depo-Provera) the requirement is at least seven days after injection, prior to test article application, or b) condom and spermicidal, or diaphragm/cervical cap and spermicidal which are effective as soon as the birth control method is administered properly. Other acceptable forms of birth control include: a) abstinence for subjects who are not sexually active or b) if the subject is in a monogamous relationship with a partner who is sterile (e.g., a vasectomy performed at least six months prior to the subject's initiation of treatment). Subjects who become sexually active or begin to have relations with a partner who is not sterile during the study must agree to use an effective form of birth control for the duration of the study.

pregnancy on the appropriate pregnancy surveillance form. The form will be sent to [REDACTED]. The investigator must notify the IRB of any pregnancy associated with the study therapy and keep careful source documentation of the event.

Protocol-required procedures for those subjects that are discontinued from the study must be performed on the subject unless contraindicated by pregnancy (e.g., x-ray studies). Other appropriate pregnancy follow-up procedures should be considered if indicated, including counseling of the subject by the investigator and her managing physician or health care provider (e.g., obstetrician). In addition, the investigator must report to [REDACTED], on the appropriate [REDACTED] pregnancy surveillance form(s), any follow-up information regarding the course of the pregnancy, including perinatal and neonatal outcome. Although pregnancy itself is not an AE, any complications during pregnancy should be recorded as AEs or SAEs (if they fulfill the SAE criteria). Offspring should be followed for a minimum of eight weeks. Any congenital anomaly/birth defect in a child born to a subject exposed to the test article(s) should be recorded as a SAE and details documented in the pregnancy surveillance form. Abortion, whether accidental, therapeutic, or spontaneous should be reported as a SAE.

15. BLINDING/UNBLINDING

This is a double-blind, randomized, placebo-controlled study. Blinding is important for the integrity of this clinical drug study. However, the blind may be broken in the event of a medical emergency in a subject, in which knowledge of the test article identity is critical to the subject's management. Before breaking the blind for a subject, the investigator should determine that the information is necessary (i.e., that it will alter the subject's immediate management). If possible, the need to break the blind should first be discussed with the responsible Medical Monitor and the best method to do this will be determined.

